1.7.2 Secondary Hypotheses

Administration of MEDI0382 SC once daily titrated up to a dose level of [REDACTED] in overweight and obese subjects with T2DM will:

- result in a reduction in energy intake versus placebo after 42 days of treatment
- result in an increase in EE versus placebo after 41 days of treatment
- result in a change in body composition (reduced body fat) versus placebo after 42 days of treatment
- result in a reduction in fasting and post-prandial glucose versus placebo after 42 days of treatment
- be well-tolerated in overweight and obese subjects

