3.2.3.2 Secondary Endpoints

Energy Intake

Given that prior studies undertaken with GLP-1 and glucagon receptor-agonists and oxm have revealed significant effects on energy intake, it is likely that MEDI0382 influences energy intake. Energy intake may be measured in a more robust way than self-report through single-blind assessment of ad libitum meal consumption.

Energy Expenditure

Given the findings of prior research describing an increase in differential components of EE it will be important to determine the effect of MEDI0382 on TEE, AEE, and REE (Section 1.2). Gold standard methodology including whole room indirect calorimetry and DLW will be used in addition to an activity monitor to obtain estimates of EE as secondary and exploratory endpoints during the study. As fluctuations in weight and fat mass may influence estimates of EE, [REDACTED] and all measurements will be adjusted for total body fat mass as measured by dual X-ray absorptiometry (DXA) scanning. In addition, subjects will be asked to abstain from caffeinated drinks for at least 24 hours prior to measurements as caffeine may increase EE and dietary advice will be given to ensure subjects have a neutral energy balance prior to whole calorimetry assessments.

Body Weight and Composition

In addition to the primary endpoint of percentage change in body weight, absolute change in body weight will also provide an overview of net energy balance versus placebo across the course of 42 days of MEDI0382 dosing.

[REDACTED]

Glucose Homeostasis

[REDACTED]

Safety and Tolerability

As MEDI0382 remains under development, safety and tolerability will be assessed throughout this study.

Standard safety endpoints including vital signs, safety laboratory analysis, treatment-emergent adverse events (TEAEs), treatment-emergent serious adverse events (TESAEs), and electrocardiograms (ECGs) will be assessed during treatment and follow-up.

[REDACTED]

Immunogenicity

[REDACTED]

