4.3.2.3 Dual X-ray Absorptiometry

The change in total body fat mass will be measured in kilograms (kg) using DXA at the beginning of the study and end of the study according to the time points specified in the schedule of treatment period study procedures (Table 6). Dual X ray absorptiometry scanning will be conducted using a Lunar iDXA scanner (GE healthcare). A single scan is equivalent to 2 days of background radiation. Subjects will be asked to remove all metal on their body and will be provided with surgical scrubs to wear when necessary. Subjects will align themselves on the scanner so that the centre of their body is lying on the middle of the scanner. Subjects will be advised to be as still as possible for the duration of the scan, which will take between 5 and 10 minutes depending on the size of the participant. There will be no requirement for sedation during the scan.

Analysis of the result will involve alignment of standard lines to outline the following sections in the body: left leg, right leg, right trunk, left trunk, right arm, left arm, and head. A read-out of the estimated mass of total body tissue, fat, and lean mass fat mass will be generated and recorded in the eCRF.

4.3.2.4

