3.4.2 Secondary Efficacy Endpoint(s) and Analyses

3.4.2.1 Secondary Efficacy Endpoint(s)

- Percentage and absolute change in total energy intake in kJ from the ad libitum lunch from Day 16 to 32 and Day 16 to 59
- Percentage and absolute change in total energy intake in kJ during the ad libitum lunch from Day -1 to 16
- Percentage and absolute change in TEE, AEE, and REE as measured by whole room indirect calorimetry in kJ per kg of fat body mass from Day 15 to 58
- Percentage and absolute change in REE as measured by hood indirect calorimetry in kJ per kg of fat body mass in kJ from Day 16 to 32
- Percentage and absolute change in total energy expenditure as measured by doubly labelled water in kJ per kg of fat body mass from baseline (Day 17) to the end of treatment (Day 58 or 59)
- Absolute change in body weight in kg from Day 17 to 59
- Change in absolute and percentage change in total body fat mass as measured by DXA in kg from Day -1 to 59
- Change in absolute and percentage change in total body fat mass: lean mass ratio as measured by DXA from Day -1 to 59
- Change in fasting glucose during a MMTT from Day -1 to 59

- Percentage change in glucose AUC_{4h} during a MMTT from Day -1 to 59

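### Whole-room and doubly labelled water energy expenditure are analysed per kg of fat mass with no stated DXA divisor; if each value uses the nearest scan, fat loss alone looks like higher expenditure

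*SAP*

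**What the plan says.** SAP 3.4.2.1, in agreement with Protocol Table 2, expresses every readable secondary EE endpoint per kg of fat mass:

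- Whole-room calorimetry, Day 15 to 58: "Percentage and absolute change in TEE, AEE, and REE as measured by whole room indirect calorimetry in kJ per kg of fat body mass".
- Hood calorimetry: "REE as measured by hood indirect calorimetry in kJ per kg of fat body mass in kJ from Day 16 to 32".
- DLW TEE: "doubly labelled water in kJ per kg of fat body mass from baseline (Day 17) to the end of treatment (Day 58 or 59").

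Protocol 3.2.3.2 gives the reason. Fluctuations in weight and fat mass may affect EE estimates, so "all measurements will be adjusted for total body fat mass as measured by dual X-ray absorptiometry (DXA) scanning". Part of that sentence is redacted.

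Fat mass is measured "using DXA at the beginning of the study and end of the study" (Protocol 4.3.2.3). Protocol Table 6 places the scans on Day -1 and Day 59. I found no statement of which scan is the divisor at each EE time point.

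Protocol 1.7.2 hypothesises that MEDI0382 will "result in a change in body composition (reduced body fat) versus placebo after 42 days of treatment" and will also "result in an increase in EE versus placebo after 41 days of treatment".

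SAP 3.4.2.3 analyses these endpoints by an ANCOVA similar to the primary one, which adjusts for treatment and baseline. SAP 3.1 sets a two-sided alpha of 0.10 with no multiplicity adjustment.

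**The concern.** If the divisor is the fat mass nearest in time, it is a post-randomisation variable that the drug is expected to lower. A smaller divisor raises the ratio, which is the direction the protocol hopes to see for EE. The placebo arm does not cancel this, because fat loss is expected to differ between arms. The ANCOVA does not cancel it either, because a baseline covariate cannot correct a divisor that changes after randomisation.

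Protocol 1.5 frames the study around whether weight loss comes from lower intake, higher expenditure or both. A ratio that rises when kJ/day is flat or falling could give the wrong answer to that question.

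**Working it through.** **The plan's own figure.** The documents give no effect size, SD or power for EE. The nearest figure is the power for weight in SAP 2.4: above 90% for a 2.5% difference, SD 2.0%, 16 versus 8, two-sided 0.10. I get 89.3% (normal approximation) or 87.5% (noncentral t, 22 df). Only the 2.5% is used below.

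**Inputs**

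- From the SAP: 2.5% weight difference, 16 versus 8 subjects, two-sided alpha 0.10.
- Assumed, because the documents are silent: fat is 35-45% of body weight, 50-100% of the weight lost is fat, and the SD of percentage change in the EE ratio is 5%, 8% or 10%.

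**Step 1: fractional fat loss.** f = 0.025 × (share of loss that is fat) / (fat fraction of weight). The lowest value is 0.025 × 0.50 / 0.45 = 2.78%. The highest is 0.025 × 1.00 / 0.35 = 7.14%.

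**Step 2: change in the ratio under a nearest-scan divisor.** With kJ/day unchanged it is 1/(1 - f) - 1. If EE truly falls 2.5%, in proportion to weight, it is 0.975/(1 - f) - 1.

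| Fat fraction | Share of loss as fat | Fat loss | Ratio, EE unchanged | Ratio, EE down 2.5% |
|---|---|---|---|---|
| 45% | 50% | 2.78% | +2.9% | +0.3% |
| 40% | 75% | 4.69% | +4.9% | +2.3% |
| 35% | 100% | 7.14% | +7.7% | +5.0% |

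Middle row as an example: 100 kg, 40 kg fat, 1.875 kg of fat lost, TEE constant at an assumed 10,000 kJ. The ratio goes from 10,000/40 = 250.0 to 10,000/38.125 = 262.3 kJ/kg. A true TEE fall of 1.875/40 = 4.7% would be hidden completely.

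**Step 3: chance of a false significant increase, kJ/day unchanged.** Noncentrality = artefact / (SD × √(1/16 + 1/8)) = artefact / (0.433 × SD). The probability is the upper tail of a noncentral t with 22 df beyond 1.717. The nominal value is 5%.

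| Artefact | SD 5% | SD 8% | SD 10% |
|---|---|---|---|
| 2.9% | 36% | 20% | 16% |
| 5.0% | 72% | 40% | 30% |
| 7.7% | 96% | 70% | 53% |

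**Step 4: does the choice of scan matter?** An ANCOVA of this type (treatment plus baseline ratio) was simulated with no drug effect on kJ/day. It assumed mean weight 97 kg, mean fat fraction 38%, 50-100% of the loss as fat, and an SD of 3-8% for EE change in kJ.

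- Divisor at each time point: spurious difference of +3.5 to +7.3 points, and a significant increase in 23-76% of trials.
- Divisor fixed at baseline: difference of about 0 (-0.02 to +0.29 points), and a significant increase in 4.7-5.9% of trials, which is nominal.

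**Step 5: hood REE, Day 16 to 32.** The only scan before Day 32 is Day -1. If it divides both values, it cancels from the percentage change and there is no artefact. Bias arises only if the Day 59 scan is applied to the Day 32 value.

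**The case against.** The strongest reply is that the documents never name the divisor. If Day -1 fat mass is used throughout, percentage change in kJ per kg fat equals percentage change in kJ, and the problem disappears. That is correct. A reader might infer that the plan as written is certain to report fat loss as increased expenditure, but the text does not support that. It supports an undefined divisor that produces bias on the more natural reading. I call that reading more natural because a change in kJ per kg of fat ordinarily means each value over its own fat mass, and because fluctuation in fat mass is the protocol's stated reason for adjusting.

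A reader might also extend the bias to every secondary EE endpoint. Hood REE does not fit, as step 5 shows. Nor does using a Day -1 scan for the Day 15 to 17 baselines bias the comparison in expectation. Both arms receive the same single-blind placebo in the run-in, so this adds noise.

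Three further points stand in part:

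- The exploratory EE endpoints are redacted, so it cannot be said that EE in kJ is analysed nowhere.
- Change in DXA fat mass is itself a secondary endpoint, so an alert reader could see the divisor shrink. That does not correct the EE test.
- The endpoints are secondary in an exploratory Phase 2a study, and the primary weight endpoint is unaffected. The mechanism is still what these endpoints are there to establish.

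**Conclusion.** The concern holds for whole-room TEE, AEE and REE and for DLW TEE, on condition that each value is divided by the nearest DXA fat mass. The ratio then rises against placebo by 2.9% to 7.7% with EE unchanged, and by 0.3% to 5.0% if EE falls 2.5%. With EE unchanged, the false-positive chance in the hypothesised direction is about 16% to 96%, against 5%. That range is wide because fat fraction, composition of the loss and EE variability are all assumed; no single value within it should be quoted as the expected rate. The direction does not depend on those values: under this divisor, the ratio avoids rising only if EE falls by at least the same percentage as fat mass.

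For hood REE the finding is narrower: the Day 32 divisor is undefined. On any reading, the plan has to say what it divides by.

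**What to change.** - Make change in EE in kJ/day the analysed endpoint for whole-room, DLW and hood measurements, including Day 32 hood REE. Use ANCOVA with treatment, baseline EE, and Day -1 DXA lean and fat mass.
- Keep kJ per kg of fat as a descriptive summary. If the ratio is retained for inference, state that the divisor is Day -1 fat mass at every time point.
- Label any model that uses lean and fat mass at each time point as exploratory, because it conditions on variables the drug may change. Limit it to Day 58/59, since there is no DXA near Day 32.

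**Cost.** No new data: Protocol 4.3.2.3 already records fat and lean mass, and kJ is the numerator of the present endpoints. The wording changes in both the SAP and Protocol Table 2, so a protocol amendment may be needed. Adding lean and fat mass to a model with treatment and baseline EE costs two degrees of freedom (residual df 21 to 19 with 24 subjects), or one if a single composition covariate is used.

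The change should be settled before unblinding.

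### Whole-room and doubly labelled water energy expenditure are divided by fat mass, which MEDI0382 is expected to lower, so fat loss alone can read as a rise in expenditure

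*SAP*

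**What the plan says.** All visible secondary energy expenditure (EE) endpoints are ratios to fat mass. SAP 3.4.2.1 and protocol Table 2 define three sets:

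- Whole-room TEE, AEE and REE, "as measured by whole room indirect calorimetry in kJ per kg of fat body mass from Day 15 to 58".
- DLW TEE, also per kg of fat, from Day 17 to Day 58 or 59.
- Hood REE: "REE as measured by hood indirect calorimetry in kJ per kg of fat body mass in kJ from Day 16 to 32".

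Protocol 3.2.3.2 identifies the divisor: "all measurements will be adjusted for total body fat mass as measured by dual X-ray absorptiometry (DXA) scanning". It gives as background that shifts in weight and fat mass may affect EE estimates; part of that sentence is blacked out.

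Protocol 1.7.2 lists among the secondary hypotheses that MEDI0382 will raise EE and that it will "result in a change in body composition (reduced body fat) versus placebo after 42 days of treatment". DXA fat mass is a secondary endpoint in its own right.

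Protocol Table 6 schedules DXA on Day -1 and Day 59 only. Each scan yields "A read-out of the estimated mass of total body tissue, fat, and lean mass", so lean mass is available too. No visible text says which scan divides which EE value.

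SAP 3.4.2.3 analyses these endpoints with an ANCOVA like the primary one, that is, treatment and baseline (SAP 3.4.1.3). SAP 3.1 sets two-sided alpha at 0.10 without multiplicity adjustment.

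**The concern.** A ratio moves when either part moves. Here the plan expects the denominator to fall more on MEDI0382 than on placebo, so success on body fat pushes the EE endpoints upwards whatever happens to expenditure. Randomisation does not protect against this, because the divisor changes after randomisation. The baseline covariate does not either, because the difference between arms arises during treatment.

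Dividing by fat mass would correct for fat loss only if EE were proportional to fat mass, which the documents do not claim.

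At stake is the reading of the EE hypothesis. Protocol 1.5 asks whether weight loss comes through intake, expenditure or both. A significant increase in EE on this scale may only restate the DXA fat result.

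**Working it through.** **The plan's own figure.** The documents give no effect size or power for any EE endpoint. SAP 2.4 gives power for the primary endpoint only: 16 vs 8, difference 2.5%, SD 2.0%, two-sided alpha 0.10, power above 90%. Check: 2.5 / (2.0 × √(1/16 + 1/8)) = 2.887; 2.887 − 1.645 = 1.242; power 89.3%. The noncentral t gives 87.5%, or 90.1% if baseline correlates 0.3 with the outcome. The figure is thus roughly reproduced. Only the 2.5% difference, the group sizes and alpha are carried forward.

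**Formula.** Let e be the true relative change in EE and f the relative loss of fat mass on MEDI0382, with placebo held flat for simplicity. Then

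change in EE per kg fat = (1 + e)/(1 − f) − 1.

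With e = 0 this is f/(1 − f). It is zero only when e = −f, that is, when EE falls by the same fraction as fat. If placebo fat also changes, the difference between arms drives the bias.

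**Which scan.** Baseline values are taken on Days 15 to 17 and final values on Days 58 to 59. Nearest-scan division therefore uses Day -1 and Day 59. For DLW the fit is close: the first dose is given on Day -1, and the last sample is due on Day 58 or 59.

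**Worked example (assumed values).** TEE is 10,000 kJ/day at both visits and fat falls from 40.0 to 37.5 kg. The endpoint goes from 10,000/40.0 = 250 to 10,000/37.5 = 266.7 kJ/kg, a rise of 6.7% with no change in expenditure.

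**Size at the SAP's 2.5% weight difference.** f = 0.025 × (share of loss that is fat) / (body-fat fraction). Both fractions are assumptions.

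| Body fat | Fat share of loss | f | EE unchanged | EE falls 2.5% |
|---|---|---|---|---|
| 35% | 60% | 4.29% | +4.48% | +1.87% |
| 35% | 75% | 5.36% | +5.66% | +3.02% |
| 35% | 100% | 7.14% | +7.69% | +5.00% |
| 40% | 60% | 3.75% | +3.90% | +1.30% |
| 40% | 75% | 4.69% | +4.92% | +2.30% |
| 40% | 100% | 6.25% | +6.67% | +4.00% |
| 45% | 60% | 3.33% | +3.45% | +0.86% |
| 45% | 75% | 4.17% | +4.35% | +1.74% |
| 45% | 100% | 5.56% | +5.88% | +3.24% |

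In plain kJ the artefact is zero.

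**Chance of a falsely significant rise.** ANCOVA on percentage change with treatment and baseline was simulated for 16 vs 8, with 3,000 trials per cell. A rise counts as significant in the upper tail of a two-sided 0.10 test, so the nominal rate is 5%. Assumed: baseline TEE 10,000 kJ (SD 1,300), baseline fat 38 kg (SD 7) independent of TEE, SD of percentage fat change 3%. The f values stop at 6.25%.

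| f | SD of % EE change | EE unchanged | EE falls 2% |
|---|---|---|---|
| 3.33% | 3 / 5 / 7% | 53.0 / 35.6 / 26.0% | 17.0 / 11.7 / 9.4% |
| 4.7% | 3 / 5 / 7% | 77.5 / 55.6 / 39.3% | 40.2 / 26.0 / 18.6% |
| 6.25% | 3 / 5 / 7% | 94.4 / 77.3 / 57.0% | 72.5 / 48.4 / 33.4% |

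The same trials analysed in kJ gave 4.7-5.6% with EE unchanged.

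**Hood REE, Day 16 to 32.** If the Day -1 scan divides both values, the divisor cancels from the percentage change and there is no artefact. If the Day 59 scan divides the Day 32 value, the artefact enters and includes fat lost after Day 32. A literal nearest-scan rule would choose Day 59, since 59 − 32 = 27 days, against more than 30 days back to Day -1. The documents do not settle which is meant.

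**The case against.** The strongest reply concerns scope and certainty.

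- **Hood REE.** A reader might infer that every EE endpoint is shown to be biased. The documents do not support that for hood REE, where the outcome depends on an unstated scan rule. For the room and DLW endpoints the bias also rests on nearest-scan division, which is the natural reading but is not written down.
- **One arm only.** A reader might infer that fat falls only on MEDI0382. Nothing says placebo fat stays constant; the hypothesis is a difference between arms, and that is enough.
- **Intake versus expenditure.** A reader might infer that the trial cannot tell the two apart. That goes too far: ad libitum intake is analysed in plain kJ, and raw EE is collected, so kJ/day can be recovered.
- **Status of the tests.** The trial is an exploratory Phase 2a study. The primary endpoint is body weight and is untouched. Speaking of falsely confirming the EE hypothesis overstates what these tests can do.
- **Redaction.** Part of the rationale sentence in protocol 3.2.3.2 and the exploratory endpoints are blacked out. An exploratory analysis in plain kJ cannot be excluded, though it would not change how the secondary endpoints are defined.
- **A slip for fat-free mass?** Protocol 3.2.3.2 names total body fat mass, so this reading fails.

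All these limits on scope and certainty stand except the last. None removes the algebra for the room and DLW endpoints.

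**Conclusion.** The point holds for whole-room TEE, AEE and REE and for DLW TEE, given nearest-scan division. Its direction is algebraic and needs no outside figure. Its size does: +3.4% to +7.7% rests on the SAP's 2.5% weight difference plus assumed body-fat and fat-loss shares. Over the same range, a true 2.5% fall in EE would still show as a rise of 0.9% to 5.0%.

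The 26-94% range for a falsely significant rise illustrates the risk and is not an estimate for this trial. The documents give no SDs for EE or fat change. The simulation describes TEE, and AEE and REE may vary differently.

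For hood REE the supportable finding is that the divisor is unspecified, not that the endpoint is biased. As defined, a significant rise in the room or DLW endpoints could not by itself be read as an increase in expenditure.

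**What to change.** In SAP 3.4.2.1 and 3.4.2.3 and protocol Table 2 (with the matching synopsis entries):

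1. Make EE in kJ/day the analysed outcome for room TEE, AEE and REE, hood REE and DLW TEE. Use ANCOVA with treatment and baseline EE in kJ/day.
2. Day -1 DXA lean and fat mass may be added as covariates, since they precede double-blind treatment. With 24 subjects this lowers the residual degrees of freedom from 21 to 19.
3. Label any model that uses change in lean and fat mass as supportive, because it conditions on a post-randomisation outcome. Limit it to the room and DLW endpoints, as there is no scan near Day 32.
4. Report kJ per kg of fat descriptively only, and state which scan divides which EE value, including hood REE on Day 32.
5. Amend the sentence in protocol 3.2.3.2 to match.

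The cost is wording in two documents; no new measurement is needed. The downside is that the EE result may look less favourable to the drug.

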3.4.2.2 Handling of Dropouts and Missing Data

Generally, both a measurement at the baseline time point and at the final time point for each endpoint are needed for a subject to be included in the analysis for change or percent change. If the measurement at the final time point for an endpoint is missing, LOCF will be used for missing data imputation if applicable.

3.4.2.3 Secondary Efficacy Analyses

The analysis of the secondary efficacy endpoints will be performed using the mITT population for endpoints comparing MEDI0382 and placebo during the double-blind treatment period. For secondary efficacy endpoints that allow comparison of MEDI0382 and placebo, the endpoints will be analyzed by an ANCOVA model similar to that used for the primary efficacy analysis. Selected secondary endpoints will also be analysed using the Per-protocol population.

3.4.3 Exploratory Efficacy Endpoint(s) and Analyses

3.4.3.1

[REDACTED]

3.5 Patient Reported Outcomes

3.5.1 PRO Endpoints

- Change in hunger and satiety scores as measured with the DEBQ restrained, emotional, and external eating factors and the 4-item visual analog scale from Day 15 to 58
- Change in total reported energy intake in kJ as recorded in a food diary from:
 - Day 16 to 32
 - Day 16 to 59

3.5.2 PRO Analyses

The analysis of the PRO endpoints will be performed using the mITT population. The patient reported outcomes (PRO) endpoints include hunger (4 self-reported items) and satiety (33

3.6 Pharmacodynamic Endpoint(s) and Analyses

3.6.1.1 Pharmacodynamic Endpoint(s)

-
- | Label | Bar Length (approx. % of total width) |
|-------|---------------------------------------|
| 1 | 95 |
| 2 | 85 |
| 3 | 65 |
| 4 | 70 |
| 5 | 100 |
| 6 | 95 |
| 7 | 65 |
| 8 | 95 |
| 9 | 100 |
| 10 | 100 |
| 11 | 55 |
| 12 | 95 |
| 13 | 90 |
| 14 | 95 |
| 15 | 100 |

[REDACTED]

3.7 Safety Analyses

The analyses of the secondary safety endpoints will be performed using the As-treated population.

